Staff assessing outcome measures are blind to treatment arm, and for some measures receive training using videotaped and practice interviews until achieving high (ICC>.80) reliability based on 20 assessments by 2 raters. We achieve high inter-rater reliability (e.g., ICC>0.85 for PANSS total), and check for rater drift each 90d.

Specific Procedures: TCT is completed with a dedicated room and equipment. Staff trained with a UCSD-developed “TCT Clinician Competence Assessment” monitor TCT, clarify instructions and provide encouragement as needed. **In the initial “biomarker testing” session (Test 1),** subjects complete 1-h of Sound Sweeps to generate a “Pre-Training APS score” as described previously (Fig. 3) under identical circumstances and timelines as for the Test 2 session described below. Treatment group assignment (PBO vs. MEM) is then made using stratified random sampling (above) and 5-7 days later patients ingest either PBO (n=27) or 20 mg MEM (n=27) 240 min before completing the Sound Sweeps session (“Test 2”). MEM effects on APS learning are assessed both within-subject (APS (Test 1 - Test 2) for MEM group subjects: a key measure of **MEM sensitivity**) and between subjects (APS Test 2, PBO vs. MEM groups). After Test 2, all subjects are prescribed daily PBO or MEM using a standard titration schedule (MEM 5 mg at hs→ 5 mg bid→ 5 mg am/10 mg hs→ 10 mg bid over 3 weeks). Participants return to the laboratory to complete 1h TCT per our established procedures^{2,34}, which includes 5 modules of auditory/verbal processing exercises. Each module increases in difficulty as performance improves: **1) Sound Sweeps; 2) Syllable Identification:** Patients distinguish between 2 similar phonemes (e.g., “ba” vs. “da”), differing only in their voice onset time; **3) Word Matching:** Subjects match short similar-sounding consonant-vowel-consonant words (e.g., bad, dad); **4) Listen & Do:** Subjects reconstruct a spoken series of instructions and use a computer mouse to click icons on the screen in a specified order. This exercise is designed to stimulate verbal WM processes supported by the lateral PFC as well as premotor and motor processes. **5)**

Table 1. “Go” criteria: #1, plus at least one of #'s 2, 3 & 4 ($d>0.5$)

1. **Target engagement:** APS learning, MEM > PBO, p<0.05
2. **Greater** clinical, neurocognitive **or** functional gains:
 - ↓PANSSt, ↑MCCB-C **or** ↑Fnxn: MEM+TCT > PBO+TCT
3. **Faster** clinical, neurocognitive **or** functional gains:

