 - drug group x session interaction ($p<0.05$) followed by MEM+TCT > PBO+TCT at specific session # or combination;
4. **More durable** clinical, neurocognitive **or** functional gains:
 - MEM+TCT > PBO+TCT at post-TCT week 12.

PANSSt: *Positive & Negative Symptom Scale total*; MCCB-C: *MATRICS Composite*; Fnxn: *Function (assessed via the World Health Organization Disability Schedule 2.0 (WHODAS))*

Rhythm Recall: Subjects listen to and replicate a short rhythmic sequence. This task is designed to stimulate both basic auditory processes supported by primary auditory cortex, and non-verbal auditory WM.

Symptoms are assessed to track clinical status and TCT response. TCT reduces positive symptoms of psychosis, and we predict that MEM will augment these effects via enhanced TCT learning (i.e. not via a lasting direct pharmacological effect of MEM), detected by the Positive & Negative Syndrome Scale. For this reason, and based on the need to limit total outcome measures, **PANSS Total Score is the primary clinical outcome measure**. Positive and negative symptom subscales, as well as PANSS factor-derived measures, will be assessed in exploratory analyses. Other secondary clinical measures will include: 1) Psychotic Symptom Rating Scales (PSRS; assesses auditory hallucinations); 2) Young Mania Rating Scale; 3) Patient Health Questionnaire-9 (PHQ-9; current depressive symptoms); 4) Abnormal Involuntary Movement Scale (AIMS); 5) **C-SSRS**; “Lifetime/Recent version” at screen; “Since Last Visit” at follow-up visits). The C-SSRS is a reliable, valid and sensitive measure of suicidal ideation⁹⁸; *any “yes” in C-SSRS prompts an immediate full evaluation/action plan by a study M.D.; and* 7) MEM Cessation Symptom Assessment (ACSA).

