Post-treatment protocol: On completion of 30 TCT sessions, participants will be offered the option of maintaining their assigned drug (PBO or MEM) through the 22-week durability assessments. Those who opt to discontinue the study drug will titrate off, over a 3-week period. After week 22, study blind will be broken, and subjects who continued to receive MEM will again be offered the option of titrating off of MEM vs. maintaining MEM treatment coordinated with, and under the supervision of, their primary provider.

Data Analysis: “Go/No Go” decisions are based on traditional statistical significance (Aim 1) and effect sizes (Aim 2). Formal statistical testing is conducted using linear mixed-effects (LME) models; hypothesis tests are 2-sided ($\alpha=.05$). Model parameters are estimated via the R lme4 package and Cohen’s d is estimated via the

EMAtools package. Type I errors are minimized by constraining the number of primary analyses; secondary analyses use false discovery rate corrections. Expected attrition rates are described above. Because outcome measures involve a “change from baseline”, baseline metrics are compared between PBO and MEM arms, and any baseline differences are addressed in the outcome analyses. Differential drop-out rates from PBO vs. MEM arms are monitored. Data are assumed to be missing at random; full information maximum likelihood estimators are used, and all data/cases are included in analyses. Clinical follow-up is pursued with all patients exiting the study through post-TCT week 12. Cohort differences: For between-subject contrasts (main effect of drug), differences in age, antipsychotic and anticholinergic loads are tested and used as covariates^{2,33,95}. Sex differences are tested for all measures. NIH Data Harmonization: 3 “PhenX Toolkit” (NOT-MH-15-009) measures of function are used; see above and “Resource Sharing Plan”.

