Aim 1 – Confirm target engagement: The primary dependent measure of target engagement is MEM-enhanced APS learning. APS learning is defined as the reduction in Sound Sweeps APS threshold (ms) Test 1 to Test 2 assessment. Target engagement was demonstrated in Fig. 3⁷⁶, and will be confirmed if APS learning is increased by MEM (note that MEM and PBO groups are matched by Test 1 PBO performance via stratified randomized assignment). As appropriate, effect sizes and inferential statistics are based on standard regression or LME models with random intercepts. A significant interaction between contrast coded drug (PBO vs. MEM) and Test (Test 1 vs. Test 2) predictors on APS learning is a “Go” criteria and confirms target engagement.

Aim 2 – Test clinical, neurocognitive and functional impact of MEM on TCT, and its relationship to target engagement: We will determine if MEM+TCT produces greater, faster or more durable clinical, neurocognitive or functional gains from baseline, compared to PBO+TCT, over a 30-session course of TCT. A Cohen’s $d > 0.5$ for the main effect of drug (PBO vs. MEM) or drug x session (#10, 20, 30) interaction in an LME model is the primary “Go” criteria. The effect of drug assesses “greater” gains. Reverse Helmert contrasts for session assesses “faster” gains. A separate model comparing differences in outcomes at 12-weeks post-TCT assesses “more durable” gains. Secondary analyses will examine whether change in MEM-enhanced APS learning (“within-subject” target engagement; Aim 1) predicts gains in Aim 2 outcome measures.

Aim 3 – Biomarkers of MEM-induced gains: We will determine if baseline levels of specific neurocognitive or EEG-based measures, or changes in specific measures with initial MEM exposure (Test 2 vs. 1), predict greater sensitivity to MEM-enhanced neurocognitive, clinical or functional gains over 30-h of TCT. Regression analyses will assess whether specific candidate biomarkers predict MEM-enhanced gains in outcome measures.

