2. MEM is not ketamine (or PCP, or MK-801). Unlike other NMDA antagonists, MEM has little impact on basal NMDA transmission¹¹⁴. In rats, PCP, ketamine and MK801 exhibit inverted-U dose-functions on spontaneous gamma power, and adversely impact other frequency bands; in contrast, gamma-enhancing effects of MEM follow a linear, positive dose-function and are selective for the gamma band⁶¹. In some behavioral measures, MEM is similar to ketamine but not PCP^{115,116}, while in others, MEM actually reverses the effects of ketamine⁴³. In measures of glutamate-dependent synaptic plasticity, MEM effects are opposite to those of ketamine and MK-801¹¹⁷. In HS, ketamine reduces MMN¹¹⁸, but MEM increases MMN ($d=0.87$)⁶². More generally, prevailing models suggest that SZ symptoms reflect NMDA hypoactivity. While these models *may* be valid at a level of cortical microcircuitry, trying to reconcile them with complex effects of oral drugs with differential effects at the NMDA receptor complex may not be useful. A cogent critique of current biological models of SZ as they relate to future therapeutics is found in, "Are we studying or treating schizophrenia correctly?"⁴¹

3. MEM is safe. The best evidence that MEM is very distinct from the PCP/ketamine class of NMDA antagonists is that MEM has been studied in >185 NIH trials, and used clinically by large numbers of elderly, frail dementia patients for years, without serious adverse events (SAEs). Unlike ketamine, which has psychotogenic effects in SZ patients¹¹⁹, studies of MEM effects in SZ patients (Table 2) have consistently reported no increased SAEs; most report beneficial effects on symptoms and cognition (including 3 meta-analyses):

Table 2. Citation	Study Design	N	mg/d	Wks	Δ Sx?	Δ Cog?	↑SAEs?
Lieberman et al. ¹²⁰	D-B RCT + SGAPs	70	20	8	∅	∅	no
Lee et al. ¹²¹	D-B RCT + APs	26	20	12	∅	∅	no
Omranifard et al. ¹²²	D-B RCT + APs	64	20	12	↑ GAF, QLS	NA	no
Veerman et al. ¹²³	D-B RCT + clozapine	52	20	12	↓ neg	↑	no
Veerman et al. ¹²⁴	1-y extension of above	24	20	52	↓ pos/neg	∅	no
De Lucena et al. ¹²⁵	D-B RCT + clozapine	21	20	12	↓ pos/neg	↑ MMSE	no
Krivoi et al. ¹²⁶	Open label	7	5-20	6	↓ pos/neg	∅	no
Rezaei et al. ¹²⁷	D-B RCT + risperidone	40	20	8	↓ neg	NA	no
Mazinani et al. ¹²⁸	D-B RCT + risperidone	22	20	12	↓ neg	↑ MMSE	no
John et al. ¹²⁹	Chart-based retrospective	26	10-20	8-100	↓ pos/neg	↑	no
Fakhri et al. ¹³⁰	D-B RCT added to olanz.	30	20	6	↓ pos/neg	NA	no
Zheng et al. ¹³¹	Meta-analysis	452	--	--	↓ neg	↑ MMSE	no

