"Go/No-Go" decisions are based on traditional statistical significance (Aim 1) and effect sizes (Aim 2). Formal statistical testing is conducted using linear mixed-effects (LME) models; hypothesis tests are 2-sided ($\alpha=0.05$). Model parameters are estimated via the R lme4 package and Cohen's d is estimated via the EMAtools package. Type I errors are minimized by constraining the number of primary analyses; secondary analyses use false discovery rate corrections.

PANSSt scores will be assessed at specific intervals. Because TCT is associated with improvements in both positive and negative symptoms, our *a priori* hypothesis is that a PACT effect will be evident in both positive and negative symptoms. Hence, PANSSt is used as the primary metric of symptomatic gains. A greater reduction in PANSSt score will be detected using data from baseline through TCT 30h, by a significant main effect of group (arm) or a significant interaction of group x session, with post-hoc contrasts revealing significant group differences at TCT 30h. A faster reduction in PANSSt scores will be detected using these same data by a significant interaction of group x session and a significant group difference at a point prior to TCT 30h. A more durable reduction in PANSSt scores will be detected using data from TCT 30h through 12 weeks post-TCT, by a significant main effect of arm or a significant interaction of group x post-TCT day, with post-hoc contrasts revealing significant group differences 12 weeks post-TCT.

Comparable analytic approaches will be used for neurocognition (MCCBc) and function (WHODAS) as described in "Research Strategy". Data will be described as means with SEM. Tests for normalcy will be applied to all data and non-parametric comparisons will be used if normalcy is not demonstrated. The Analysis Set for these data will be all subjects who have completed 30h of TCT and post-TCT clinical, neurocognitive and function assessments. When appropriate, missing data are handled via multiple imputation or full information maximum likelihood estimation.

Secondary regression analyses assess the predictive value of putative biomarkers on clinical, neurocognitive or functional gains from the addition of MEM to TCT. Future studies with larger samples will assess potentially more informative models, e.g. Path Analysis to study moderating effects of APS MEM sensitivity and biomarkers on both indirect (moderated-mediation) and direct paths between treatment and outcome.

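### The week-12 'more durable' Go criterion compares arms while patients may still be taking study drug, so it measures assignment with optional continuation, not durability of training gains

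*Combined protocol and SAP*

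**What the plan says.** **Drug after training.** The Post-treatment protocol (Research Strategy, Approach) says that after 30 sessions "participants will be offered the option of maintaining their assigned drug (PBO or MEM) through the 22-week durability assessments". For the others: "Those who opt to discontinue the study drug will titrate off, over a 3-week period". The blind is kept until after week 22.

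**The criterion.** Table 1, item 4, defines more durable gains as "MEM+TCT > PBO+TCT at post-TCT week 12", on PANSS total, MCCB composite or WHODAS. The Table 1 rule is "1, plus at least one of #'s 2, 3 & 4 ($d>0.5"; the text on Go decisions also requires that adverse effects on memantine not be significantly greater than on placebo.

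**The models.** Data Analysis, Aim 2, says: "A separate model comparing differences in outcomes at 12-weeks post-TCT assesses" durability. Section 4.4 describes a more durable PANSS reduction as "detected using data from TCT 30h through 12 weeks post-TCT, by a significant main effect of arm" or by a group by post-TCT day interaction, with significant group differences at 12 weeks, and applies a comparable approach to the other two outcomes. Neither account has a term, stratum, estimand or sensitivity analysis for drug status after training.

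**The intended mechanism.** The Symptoms paragraph predicts benefit through enhanced learning, "not via a lasting direct pharmacological effect of MEM". The answer on memantine safety says of the studies in Table 2 that "most report beneficial effects on symptoms and cognition"; the text after that table notes that none of them paired the drug with a systematic cognitive intervention.

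**A second account of dosing.** Sections 4.2.a and 4.4 describe a dose 60 minutes before each training session and mention no dosing after training ends.

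**The concern.** In this plan, durability means that what was gained in training persists after training. At week 12 the memantine arm is a self-chosen mixture: some patients still take the drug, and others stopped and, after a 3-week taper, have been off it for about 9 of the 12 weeks. An arm difference at that visit could come from retained training gains, from a drug effect in those still taking it, or from both. The planned contrast cannot tell these apart, yet Table 1 gives it the durability label.

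What is at stake is the claim carried into the confirmatory trial. If item 4 is the Aim 2 criterion that is met, the reader is told that augmented training has lasting benefit, when the data may show only that the drug helps while it is taken. That difference would affect how a later trial treats drug use during follow-up and what it claims.

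**Working it through.** **The plan's own figure.** The documents give no power or sample size for the durability criterion. The 27 per group belongs to Aim 1. It reproduces as a change-score comparison (d=0.5, r=0.8, two-sided 0.05, 80% power): 2 x (1.960+0.842)^2 x 2(1-0.8) / 0.5^2 = 25.1 before rounding up, and 27 is the smallest n reaching 80% with the t distribution. It says nothing about item 4.

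**Passages side by side.** Continuation is the patient's choice (Post-treatment protocol). Item 4 and both models compare arms at week 12 without reference to that choice. The conclusion about the label follows from these passages alone; the figures below only illustrate its possible size.

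**Inputs.**
- From the documents: 18 per arm (conservative number of TCT completers, Subject throughput) and the Go threshold of d=0.5.
- Assumed, not in the documents: share f of the memantine arm still on drug at week 12; direct effect delta, in SD, while on drug; no lasting training gain; no residual drug effect in those who stopped; one outcome.

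**Formulas.** Expected week-12 contrast = f x delta. Standard error of d is about sqrt(2/18) = 0.333. P(observed d >= 0.5) = 1 - Phi((0.5 - f x delta)/0.333).

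| f | delta | f x delta | (0.5 - f x delta)/0.333 | P(d >= 0.5) |
|---|---|---|---|---|
| any | 0 | 0 | 1.50 | 6.7% |
| 30% | 0.1 | 0.03 | 1.41 | 7.9% |
| 70% | 0.2 | 0.14 | 1.08 | 14.0% |
| 70% | 0.3 | 0.21 | 0.87 | 19% |
| 70% | 0.5 | 0.35 | 0.45 | 33% |

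The noncentral t distribution gives slightly higher values (7.1% instead of 6.7% with no effect).

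**Under section 4.4's significance wording.** With 34 degrees of freedom, p<0.05 needs d of about 2.03 x 0.333 = 0.68. A simple week-12 test then favours memantine in 2.5% of trials with no effect, and in about 9% and 17% at contrasts of 0.21 and 0.35. The distortion remains but is smaller.

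**What these figures are not.** They are chances of meeting item 4 on one outcome, not chances of a Go. Item 4 accepts any of three outcomes, which raises them. A Go also needs item 1 and the adverse-effect condition, which lowers them.

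**The case against.** **The contrast is randomised and blinded.** This stands. As long as all randomised patients are analysed, the week-12 difference validly estimates the effect of assignment with optional continuation. The fault lies in the label.

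**Item 4 does not decide a Go.** A reader might infer that item 4 can deliver a Go by itself. It cannot: target engagement must be significant and adverse effects must not be in significant excess. Item 4 can only be the sole Aim 2 criterion met.

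**The confound is not peculiar to week 12, and it is disclosed.** Items 2 and 3 also cannot separate a direct drug effect from augmented training. The answer headed No control groups names memantine use independent of TCT, calls it very unlikely and gives reasons for omitting that control. With the whole arm on drug and a direct effect of 0.3-0.5 SD, a simple session-30 contrast would exceed d=0.5 in 27-50% of trials. So item 4 is not the main route by which a direct effect could produce a Go. But items 2 and 3 are labelled greater and faster gains on treatment, whereas item 4 alone claims persistence.

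**A direct effect may be small.** This partly stands. Of the 11 individual studies in Table 2, cognition improved in 4, was unchanged in 4 and was not available in 3. The meta-analyses report negative symptoms and MMSE, not this trial's primary outcomes, and the plan itself calls the drug's clinical impact modest. The lower rows of the table may therefore be nearer the truth, and a reader should not take 19-33% as an estimate.

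**The mechanism statement contradicts nothing.** This stands: it is a prediction about symptoms and conflicts with neither the continuation option nor Table 2. The point is that item 4 cannot test it.

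**An off-drug check would be worse.** Requiring consistency in patients off drug might look like the natural repair. At 70% continuation it would leave 18 x 0.30 = 5.4 per arm, with a standard error of d of sqrt(2/5.4) = 0.61, and stopping may follow poor response or tolerability. It should not decide a Go.

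**Conclusion.** The point holds as one about what is estimated and claimed. Item 4 and its models describe a week-12 arm contrast as durability of gains, while the Post-treatment protocol leaves drug use up to that visit to patient choice. The contrast is valid for assignment with optional continuation and cannot show persistence of training gains as distinct from an ongoing drug effect.

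The size is unknown. Under the stated assumptions, the chance of crossing d=0.5 on one outcome with no lasting training gain runs from close to the 6.7% no-effect level (8-14%) up to 19-33%, and it is lower under section 4.4's significance wording. A reader might infer that a false Go is likely or that the week-12 comparison is invalid. The documents support neither: they give no continuation share and no direct effect on these outcomes, and the arms are compared as randomised. This is a cheap improvement to the plan and does not invalidate the design.

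**What to change.** 1. In Table 1 item 4, Data Analysis Aim 2 and section 4.4, keep the randomised week-12 contrast, name it as the effect of assignment with optional continuation of study drug, and limit the Go wording to that.
2. Use the medication data that General Methods already says are recorded to report, by arm, the share on and off study drug at week 12 and the session-30 to week-12 change by drug status. Mark this as descriptive, non-randomised support.
3. Do not make the Go conditional on the off-drug subgroup.
4. Reconcile the Post-treatment protocol with sections 4.2.a and 4.4, which describe only pre-session dosing. No change to the continuation option or to dosing is proposed.

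The cost is a wording change in three places and one descriptive table. The downside is a narrower claim: a Go resting on item 4 would no longer assert that training gains last without the drug.

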Measuring Target Engagement: Auditory Processing Speed (APS) Learning is the target to be engaged in this application. APS is tested via the TCT “Sound Sweeps” training exercise (Posit Science; brainhq.com): a frequency discrimination time-order judgment task^{66,67}. Subjects hear pairs of frequency-modulated sound sweeps and indicate whether they perceive each sweep as becoming higher or lower in pitch (Fig. 3). Sweep duration, frequency range and interstimulus interval get shorter after correct responses, but longer after incorrect responses. APS is calculated based on the shortest duration of stimuli that subjects discriminate correctly. Before and after each training session, subjects complete an APS assessment to quantify simple auditory learning (**APS pre- minus post-training**)²⁹. This “auditory learning” is believed to be a critical component of TCT-based clinical and neurocognitive gains and **serves as our operational measure of target engagement**^{26,30,68}.

Memantine acutely enhances APS learning: Our preliminary findings provide evidence of target engagement for this PACT model: compared to PBO, one dose of MEM (20 mg) was associated with greater APS “learning” across 1-h of a “Sound Sweeps” training session of TCT. Consistent with our previous report of amphetamine (10 mg), MEM did not alter APS, but it significantly enhanced auditory learning over 1-h of training in both HS and SZ patients, and these gains in learning were not state-dependent and lasted at least 1 week⁴³.

[figure not shown]

Fig. 3. MEM effects on Sound Sweeps learning. A. Subjects identify “sweep direction” of frequency modulated tones; adaptive trials increase in difficulty as subject learns. B. Auditory Processing Speed (APS, in ms; smaller # = better discrimination) is calculated both pre- and post-training. APS “learning” is defined as “APS pre minus APS post”. C. In a within-subject design, 20 mg MEM significantly enhanced APS learning in SZ patients (diagnosis by drug: F=5.0, p<0.035). D. MEM-induced gains in APS learning “carried forward” to pre-testing 1 wk later; this did not happen if either no pill or PBO was received the previous week (Order: F<1.0; drug: F=4.95, p<0.04); order by drug (F<1.0). Thus, MEM-enhanced learning is not “state-dependent”.

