General Methods: Environment: Subjects are screened, tested and undergo TCT at the UCSD Medical Center. Participants are 18-55 y.o. AP-medicated (stable regimen \geq 1 month, in active outpatient treatment) patients with a primary diagnosis of SZ or schizoaffective disorder (depressed type), recruited and consented at UCSD as per^{49,59,74}. Study inclusion/exclusion criteria are detailed in "**Protection of Human Subjects**". Screening includes a confirmatory diagnostic assessment (M.I.N.I. 6.0), a general medical, psychiatric and substance history, physical exam by an M.D., EKG, vision and hearing tests, urine toxicology and pregnancy test (UTox/P). All medications and changes are recorded (AP doses in chlorpromazine equivalents; quantifying anticholinergic burden⁹⁵ as in^{33,48,49}). Medication patterns of our last \approx 100 SZ subjects are published elsewhere^{49,74,96}.

Design (Fig. 5). Enrolled patients complete clinical, neurocognitive and functional measures and candidate biomarkers (EEG, QuickSIN, WIN) tested in Sound Sweeps at baseline, and then assigned to PBO vs. MEM arms (n=27/arm) using stratified random sampling (over sex, age and high/low Test 1 (baseline) APS learning) blind to arm identity. Stratifying for baseline APS learning should increase the sensitivity of the primary target engagement metric. Test 2 follows \approx 5-7 days later, after either PBO or MEM (20 mg po). Tests 1-2 are used to assess target engagement (Aim 1: MEM-enhanced APS learning) as well as MEM effects on ERP/EEG, auditory discrimination (QuickSIN, WIN) and neurocognitive measures (Aim 3: Biomarkers). Our design allows for 20% attrition from enrollment (n=69) to completion of target engagement testing (n=54).

For Aim 2, all participants will be titrated up to 20 mg MEM or Placebo over a 3-week period and concurrently begin TCT 3 d/week (M-W-F) for 1-h/d (recognizing the need for flexibility, T-Th are "make-up days"), and continues until a subject completes 30-h (\approx 10-12 weeks). TCT is delivered by trained staff (see below). Patients and staff are blind to study arm; staff are blind to patients' baseline, interval, and post-intervention assessments.

[figure not shown]

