Outcome and “Go Decisions”. In addition to confirming “target engagement”, this application tests the hypothesis that SZ patients given MEM +TCT will exhibit greater, faster and/or more durable improvements (change from baseline) in symptoms, neurocognition and/or function compared to patients given PBO+TCT, and that this enhanced clinical response will be associated with greater MEM-enhanced TCT learning.

The small “n” necessitated by the 3-year timeline and demanding treatment schedule greatly constrains the total number of outcome measures.

Moreover, the plan to assess not only magnitude but also rate and durability of PACT gains triples the number of primary analyses. Thus, we selected only one **primary** clinical, neurocognitive and functional outcome measure (Table 1) – recognizing that they are relatively “blunt” metrics - but will track several other, more focused, measures as well as inter-measure correlations in exploratory analyses to inform future studies.

A “Go” decision requires: 1) confirmation of target engagement (APS learning, MEM>PBO, p<0.05); 2) evidence of gains from PACT ($d \geq 0.5$ (MEM > PBO)) in primary clinical, neurocognitive and/or functional measures (Table 1), and 3) the absence of adverse effects of MEM that are significantly greater than PBO levels. The decision to not use traditional statistical significance as “Go” criteria for Aim 2 reflects this RFA’s call for “Pilot” studies, the need to identify candidate treatments for a subsequent larger “n” Confirmatory Efficacy R01 study, and the limits in sample size resulting from the 3-year R33 duration. Cohen defined a medium effect size ($d=0.5$) as one that is “visible to the naked eye,” and this amount of change is viewed as clinically meaningful in trials targeting negative symptoms.⁹⁹⁻¹⁰¹ This $d=0.5$ “Go” threshold for Aim 2 corresponds to a “number needed to treat” (NNT) value ≈ 3.62 . While a “Go” decision does not require identification of a biomarker predicting greater PACT sensitivity (Aim 3), the identification of one or more meaningful predictors that could be incorporated into a Confirmatory Efficacy trial would favorably impact a “Go” decision.

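### The Aim 1 analysis text defines APS learning as a Test 1-to-Test 2 threshold change, which contradicts the within-session score that the rest of the plan uses for this required Go criterion

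*Combined protocol and SAP*

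**What the plan says.** All places below are in the Research Strategy unless a section number is given.

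- **Data Analysis, Aim 1:** "APS learning is defined as the reduction in Sound Sweeps APS threshold (ms) Test 1 to Test 2 assessment". The paragraph then makes a significant drug (PBO vs. MEM) x Test (1 vs. 2) interaction on APS learning the Go criterion, and refers to Fig. 3 as the earlier demonstration of target engagement.
- **Measuring Target Engagement:** before and after each training session, "subjects complete an APS assessment to quantify simple auditory learning", taken as APS pre minus post training. This score "serves as our operational measure of target engagement". The Fig. 3 legend gives the same definition.
- **4.3 Outcome Measures:** the primary APS learning outcome is based on APS measured before and after the Sound Sweeps session.
- **Design, 4.2.a and 4.4:** arms are assigned after Test 1 and before Test 2, stratified on high or low Test 1 APS learning. The stated reason is that "Stratifying for baseline APS learning should increase the sensitivity of the primary target engagement metric".
- **Specific Procedures:** Test 1 is said to generate a "Pre-Training APS score", with a reference to Fig. 3. Memantine effects on APS learning are then written as APS (Test 1 - Test 2) within the MEM group, called MEM sensitivity, and as APS at Test 2 between arms.
- **Outcome and Go Decisions:** a Go requires "confirmation of target engagement (APS learning, MEM>PBO, p<0.05"). Table 1 lists this as criterion 1, which must be met together with at least one of the others.

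**The concern.** The defining sentence in the analysis section describes a different variable from the one named as the operational measure and listed as the primary outcome. Taken literally, it gives each patient one number, a change in threshold between two visits about a week apart. The other definition gives each patient two numbers, the gain over an hour of training at each visit.

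An analyst who works from the Data Analysis section could therefore test the wrong variable on a criterion that decides whether the programme proceeds. Because the sentence does not say which threshold is meant, it also leaves room to choose after the data are seen. The same ambiguity affects MEM sensitivity, which the plan later uses as a candidate predictor of Aim 2 outcomes.

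**Working it through.** **1. The plan's own sample size.** Inputs from Power analyses (Research Strategy and 4.4): d=0.5, two-sided alpha 0.05, 80% power, test-retest r=0.8, 27 per arm. For a between-arm contrast of change between two tests, in SDs of the score, the variance of the change is 2(1-r) = 2(0.2) = 0.4.

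- Normal formula: n = 2 x 0.4 x (1.960+0.842)^2 / 0.5^2 = 25.1, so 26 per arm. Using the t distribution gives 27.
- Power at 27 per arm: noncentrality = 0.5 / sqrt(0.4 x 2/27) = 0.5/0.172 = 2.90 on 52 df, power 0.81.

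The stated figure reproduces. It assumes one score at each of two tests, but the documents do not say which score r and d describe, so this step does not settle the definition.

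**2. Can the planned interaction be run on the variable as defined?** The model has four fixed terms: intercept, drug, Test and drug x Test.

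- One Test 1-to-Test 2 value per patient: Test does not vary, the design matrix has rank 2 of 4, and the interaction cannot be estimated.
- One within-session value at each test: rank 4 of 4, and the interaction can be estimated.

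**3. Can the stratification use the variable as defined?** Assignment comes before Test 2. A Test 1-to-Test 2 change does not exist at that point, but a Test 1 pre-minus-post score does.

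**4. What each reading would test.** Write learning at test k as L_k = pre_k - post_k. Suppose memantine adds an amount D (ms) to learning at Test 2 and leaves pre-training APS unchanged. The pilot suggests the second condition: "MEM did not alter APS, but it significantly enhanced auditory learning over 1-h of training". Carry-forward to the next week's pre-test was seen after memantine, but "this did not happen if either no pill or PBO was received the previous week", and every patient takes placebo at Test 1.

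| Variable | Expected arm difference (MEM - PBO) |
|---|---|
| L_2 - L_1 (within-session learning, drug x Test) | D |
| pre_1 - pre_2 | 0 |
| post_1 - post_2 | D |

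- Pre-training reading: with an expected difference of 0, a two-sided 0.05 test is significant in the memantine direction with probability 0.05/2 = 2.5%, whatever D is. A simulation of 40,000 trials gave 2.4%. Because it sets the drug effect on pre-training APS to zero, it only confirms the test's level.
- Post-training reading: the same difference in ms. Precision depends on the variances and on the within- and between-session correlations of the thresholds. The documents give none of these, so a gain or loss of power cannot be computed.

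**5. Sign of MEM sensitivity.** APS (Test 1 - Test 2) is positive for improvement if APS is a threshold. If it stands for APS learning, the subject of that sentence, it becomes L_1 - L_2, and a patient who learns more on memantine gets a negative value.

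**6. Optional adjusted test.** Comparing L_2 between arms, adjusted for continuous L_1, sex and age stratum, has variance 1 - r^2 = 1 - 0.64 = 0.36. Noncentrality = 0.5 / sqrt(0.36 x 2/27) = 0.5/0.163 = 3.06 on 49 df, power 0.85 against 0.81 for the interaction. Both assume that r=0.8 and d=0.5 describe the learning score.

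**The case against.** The best defence is that no careful analyst would be misled. The sentence after the definition refers to Fig. 3, whose legend gives pre minus post. Specific Procedures also refers to Fig. 3 when it mentions the pre-training score, and Fig. 3 reports APS both before and after training. This stands: the within-session score is plainly intended. A reader might infer that the endpoint is open or unspecified, and the documents do not support that.

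A second defence is that a mixed model of the raw threshold makes drug x Test equal to the arm difference in Test 1-to-Test 2 reduction, so the paragraph could be run. Such a model can be estimated. But the paragraph specifies the interaction on APS learning, not on the threshold. The threshold model would still test a different variable from the operational measure and the listed primary outcome, and would still leave pre versus post unstated.

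Third, no passage asks for an analysis of pre-training thresholds, and the 2.5% treats a pilot null as an effect of exactly zero. That is fair. The figure describes one possible misreading under one condition and does not forecast the trial.

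Fourth, the sign in Specific Procedures can be read as shorthand for a comparison. It can, but MEM sensitivity is to be used as a predictor, so its direction should be explicit.

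**Conclusion.** The concern holds as an error in the defining sentence of the Aim 1 analysis, with matching loose wording in Specific Procedures. It should be fixed because the variable is a primary endpoint and a required Go criterion.

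The size depends on the reading. With pre-training thresholds, and if memantine leaves pre-training APS unchanged, the chance of meeting the criterion in the memantine direction is about 2.5% regardless of the effect on learning. With post-training thresholds the expected difference is about the same and the effect on precision is unknown.

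A reader might also infer that Aim 1 is underpowered or that 27 per arm is wrong. The documents do not support this: the figure reproduces at d=0.5 and r=0.8, and nothing in them shows that r for the learning score is lower. Saying which score r and d refer to is a reporting point only.

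**What to change.** 1. In Data Analysis, Aim 1, define APS learning as APS pre minus APS post training within a session, scored at Test 1 and at Test 2. Keep the drug x Test interaction on that score as the single Go test.
2. In Specific Procedures, write APS learning in place of APS in both contrasts. Define MEM sensitivity as Test 2 minus Test 1 learning, so that a larger value means more learning on memantine.
3. Optional, at no cost in data: make the Go test a comparison of Test 2 learning between arms, adjusted for continuous Test 1 learning and the sex and age strata. If this is adopted, name it in advance in place of the interaction.
4. For reporting only: in both Power analyses paragraphs, say which score r=0.8 and the effect sizes describe.

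The cost is a few sentences. Both APS scores are already collected at each session, and 27 per arm is unchanged.
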